### PURSUIT Protocol Synopsis

Study Objective	A Registry to Further Develop the Understanding of the Real World use of the Eclipse™ System for Fecal Incontinence in Women
Study Design	A prospective, open label post-market registry to collect Patient Reported Outcomes and Fitting metrics (e.g. sizes used) in subjects using the Eclipse System in a commercial setting
Sites/ Subjects	Up to 150 subjects enrolled, in up to 25 sites
Study Population	All adult female patients with Fecal Incontinence who present at, or are identified at, participating sites are eligible. This includes patients who are newly prescribed Eclipse, and those already using Eclipse who return for an annual renewal visit during the enrollment period.
Study Duration	Per-patient registry participation will last one year from the date of Eclipse fitting. Sites will be allowed to enroll patients until the earlier of: 12/31/2019 or enrollment of 150 patients.
Outcomes Measures	

1. Fitting Metrics

2. Change from baseline in mean scores on subject-reported outcomes related to symptoms as reported by St. Mark's (Vaizey) Incontinence Severity Score

3. Eclipse Experience Feedback Assessment, including the Patient Global Impression of Improvement (PGI-I)

Eligibility Criteria	

1. Adult female

2. Diagnosis of Fecal Incontinence

3. Clinician recommendation of the Eclipse System

4. Subject provides informed consent and HIPAA authorization

# 1 Background

---

## 1.1 Feasibility Studies

Two feasibility studies were initially conducted to assess the fit and function of the Eclipse System in female subjects. These studies were approved by each site's Institutional Review Board (IRB) as non-significant risk (NSR) device investigations. In total, 86 subjects were fit with the Insert who wore it for up to 3 months. Initial safety and effectiveness outcomes were deemed acceptable for ongoing study.

## 1.2 LIFE Pivotal Study

The LIFE Study (Protocol CA003) was a multi-center, prospective, open label clinical trial conducted at 6 centers in the United States. As with the prior studies, all IRBs approved the trial as an NSR investigation. The objective of this pivotal trial was to evaluate the safety and effectiveness of the Eclipse System for the treatment of Fecal Incontinence (FI) in adult women.

Sixty-one (61) subjects met all study eligibility criteria and entered the 1-month Treatment Period to make up the Intent to Treat Cohort. The primary effectiveness endpoint was met: At 1 month, 78.7% of the ITT Cohort (95% CI, 66-88%,  $p < 0.0001$ ) met the success criterion, defined as a 50% or more reduction in the number of FI episodes. Additionally, there were no serious device-related adverse events reported in the trial.

## 1.3 LIBERATE

The LIBERATE study was a multi-center, prospective, open label clinical trial conducted at 11 centers in the United States. As with the prior studies, all IRBs approved the trial as an NSR investigation. The objective of this study was to evaluate the safety and effectiveness among treatment responders between 3 and 12 months.

Seventy-three (73) subjects met all study eligibility criteria and entered the 12-month Treatment Period to make up the Intent to Treat Cohort. The primary effectiveness endpoint was met: At 3 months, 73% (95% CI 61-82%,  $p < 0.0001$ ) of subjects met the success criterion, defined as a 50% or more reduction in the number of FI episodes. At 12 months, 70% (95% CI 58-80%,  $p < 0.0001$ ) met the success criterion. Additionally, throughout the study there were no serious device-related adverse events reported.

## 1.4 LIBERATE PRO

The LIBERATE PRO registry study is an on-going, prospective, open label post-market registry to collect patient reported outcomes in subjects using the Eclipse System after completing the LIBERATE study. Patients who completed LIBERATE were offered new Eclipse devices to be used in the subsequent year, and were offered enrollment in LIBERATE PRO in which they would complete online surveys at 3, 6, 9, and 12 months. As the registry database was hosted and maintained by Pelvalon (sponsor) and no clinic visits were required of the patients, Pelvalon was the only site to seek and obtain IRB approval.

Eighteen (18) patients enrolled in the registry and completed one or more surveys. All but 2 patients have completed their participation and there have been no adverse events reported as part of LIBERATE PRO.

## **1.5 Description of the Eclipse System**

### **1.5.1 Overview**

The Eclipse System is a vaginal bowel control (VBC) therapy intended to provide bowel control for women with fecal incontinence. Manufactured by Pelvalon (Sunnyvale, CA), it is comprised of a non-surgical device placed in the vagina (referred to as the “Eclipse Insert”) and a pressure-regulated pump which is used to inflate and deflate the Insert.

### **1.5.2 The Sizing Kit**

The Sizing Kit is a set of reusable fitting inserts (Sizers) which consist of the same stainless steel base and medical grade silicone coating as the Eclipse Insert, but without the balloon that is part of the Eclipse system. These reusable Sizers are available in the same base sizes as the Eclipse Insert, and can be reused after reprocessing in accordance with the Instructions for Use (IFU).

### **1.5.3 The Trial Insert**

Prior to providing the Eclipse Insert to a subject, the clinician will use the Sizers and the Trial Insert to assess appropriate fit of the Eclipse Insert for each subject. The Trial Insert is composed of a base made of medical grade silicone, polycarbonate, and stainless steel, and a balloon made from medical grade silicone and polyurethane.

[figure not shown]
The Trial Insert consists of base-balloon configurations sized exactly as the Eclipse Inserts are sized and is intended for short-term use (1-2 weeks). This disposable Trial Insert allows the subject to try one or more Insert sizes (while keeping a fecal incontinence episode diary) during the Fitting Period before qualifying for and committing to the year-long use of the Eclipse Insert.

A silicone inflation tube connects to the balloon on one end, and to a self-closing luer valve (Valve) and cap on the other end which extends outside of the subject’s vagina. An optional extension tube can be added between the existing tube and the Valve to increase the length. The Valve allows the user to inflate or deflate the balloon with the Pump.

### **1.5.4 The Eclipse Insert**

The Eclipse Insert is provided as a non-sterile unit for use by a single patient and is currently available in a range of base sizes with two (2) different balloon sizes. It is composed of a base made of medical grade silicone and stainless steel, and a balloon made of medical grade silicone and polyurethane. The Eclipse Insert is graphically depicted in **Figure 1**.

A silicone inflation tube connects to the balloon on one end, and to a self-closing valve (Valve) and cap on the other end which extends outside of the subject’s vagina. The Valve allows the user to inflate or deflate the balloon with the Pump. An optional extension tube can be added between the existing tube and the Valve to increase the length.

[figure not shown]

**Figure 1. Eclipse Insert (inflated state)**

### 1.5.5 The Pump

A pressure-regulated Pump (**Figure 2**) is provided to inflate and deflate the Insert. The Pump connects to the Insert via the Valve. The Pump has two ports that connect to the Valve: one end for adding air (labeled with a "+") and the other end for removing air (labeled with a "-"). Air is moved through the Pump by squeezing the pump body. During inflation, the Pump is squeezed seven to ten times. Seven pumping motions are required to adequately fill the balloon. The balloon will not over-inflate because any excess air is vented out by the regulator. When the balloon is fully inflated, the internal pressure is set to the venting pressure of the regulator.

Regulators are removable so that different balloon pressures can be achieved. Regulators and pumps are also designed for single-patient use only. Three different Regulators are available that regulate the balloon pressures to within the values listed in **Table 1**. The Pump is packaged with a Medium regulator attached. The Low and High Regulators may also be shipped separately.

**Figure 2. Pump**

**Table 1. Regulators and Associated Pressures**

Regulator	Pressure at Full Inflation (mmHg)
Low	45-57
Medium	70-92
High	114-129

[figure not shown]
## **1.6 Mechanism of Action of the Eclipse System**

The Insert is placed in a position similar to other vaginal devices, such as diaphragms, pessaries, and tampons, whose safety profiles are well-established. Insertion and removal, and inflation and deflation of the Insert, are under the control of the subject.

The Insert is designed to restore bowel continence in women with FI by replacing the normal continence function provided by the rectum and anal canal, which is complex and multi-factorial. The Insert utilizes the naturally overlapping potential spaces of the vagina and rectum to inhibit (or allow) stool passage in a user-controlled manner. Though separated by the conformable rectovaginal septum, much of the vagina and rectum effectively share the same space. When the rectum fills with stool, it expands, taking up more of this shared space. This is often palpable on a vaginal exam as the vagina conforms to the shape of the expanded rectum. Similarly, when an object is placed in the vagina, it is often palpable in the rectum. The redundant nature of the vaginal tissue makes it naturally conformable without discomfort or strain.

The Insert is designed such that when it is placed in the vagina and is in the deflated state, the rectal space is not occupied, allowing stool to pass through normally (see **Figure 3**, left). When the Insert is inflated, the vagina conforms around it, causing a reduction in rectal space, which helps the patient prevent unwanted stool passage (see **Figure 3**, right).

In **Figure 4** the Insert is shown in its deflated state. The base of the Insert is flexible to allow for ease of insertion and removal, as shown in **Figure 5**.

[figure not shown]

**Figure 4. Deflated balloon**

**Figure 5. Folded Insert**

### **1.7 Regulatory Status of the Eclipse System**

The Eclipse System received marketing clearance from the U.S. Food and Drug Administration (FDA) on November 12, 2015.

### **1.8 Indications for Use**

The Eclipse System is indicated for the treatment of fecal incontinence in adult women.

## **2 Current Study Description**

---

### **2.1 Study Design**

PURSUIT is a prospective, open label post-market registry to collect Fitting metrics (e.g. sizes used) and Patient Reported Outcomes in subjects using the Eclipse System in a commercial setting.

### **2.2 Target Population**

Up to 150 subjects may be enrolled. All women being approached for inclusion into the PURSUIT registry must be adult female patients at participating sites and must have a diagnosis of Fecal Incontinence. She must be a new user of Eclipse or a patient returning to the clinic for her annual f/u visit. All participants will be required to provide informed consent and HIPAA authorization.

### **2.3 Recruitment and Enrollment**

All patients who are deemed new suitable clinical candidates for the Eclipse System at a participating site will be invited to participate, as well as patients who are already using Eclipse, and return for an annual renewal visit during the enrollment period.

Potential subjects will be presented with information about how to sign up for the registry. . Each subject will be directed to a study-specific URL (searchable web page) where they can read an electronic Informed Consent Form and HIPAA Authorization Form. If they click on the "I agree to participate", "I consent", or similarly worded button they are taken to a registration form and are asked to provide their full name, date of birth, address, phone number and email address.

By navigating to and completing the registration page, this signifies the subject's willingness to participate in the online surveys and to receive future emails with the links to the online surveys to be completed, as well as to be contacted by the Sponsor by phone, email or in writing to remind

them to complete the surveys, and/or to provide clarifications about the information they have been provided in the completed surveys.

If a subject does not have access to, or is unwilling to provide, an email address, they can review a paper version of the Informed Consent Form and HIPAA Authorization form, and will be given an option to receive paper versions of all study surveys which can be filled out by hand and mailed back to the Sponsor. Similarly, if a site cannot easily access the URL, they can use the paper versions of all forms / surveys as well.

Enrollment in the post market registry, including the online data capture, will last for up to one year, and recruitment will end on 12/31/2019 or after 150 patients have been enrolled.

Sites will receive compensation for completing site surveys at each patient visit. Subjects will receive compensation for their time to complete each online (or returned hard copy) survey, which will be outlined in the Informed Consent form.

Enrollment will be completed once the annual visit is complete (approximately 1 year after enrollment begins).

## 2.4 Schedule of Events

At the Enrollment/Fitting visit, and subsequent in-office visits (as outlined below, in **Table 2**), patients and clinicians will access online surveys to complete the required data collection (or if necessary, use hard copies). Additionally, subjects will be sent an email with a link to the optional 3, 6, and 9 month surveys or mailed printed surveys, depending on chosen survey delivery method, to be completed at each of 3, 6, and 9 month time points as per the schedule in **Table 2**.

**Table 2. Schedule of Events**  
(shaded columns indicate in-office visits)

	Enrollment / Fitting	Subsequent Fittings (if necessary)	Eclipse Visit	3 Mo	6 Mo	9 Mo	12 Mo
Informed Consent & HIPAA Authorization	X						
Bowel Health History	X						
Fitting Metrics	X	X	X				X
St. Marks (Vaizey) Assessment	X		X	X	X	X	X
Eclipse Experience Assessment (including PGI-I)		X	X	X	X	X	X

## 2.5 Surveys

The following questionnaires or surveys will be collected (as outlined in Table 2, above):

### 2.5.1 Bowel Health History

The Bowel Health History survey collects information regarding the patient's history with FI (symptoms and treatments), as well as other bowel health items, such as IBS and Rectal Prolapse. Also included are marketing questions about Eclipse and health insurance.

CONFIDENTIAL - THIS DOCUMENT CONTAINS CONFIDENTIAL AND PROPRIETARY INFORMATION THAT IS THE PROPERTY OF PELVALON, INC. NEITHER THIS DOCUMENT NOR THE INFORMATION HEREIN MAY BE REPRODUCED, USED, OR DISCLOSED TO ANY THIRD PARTY WITHOUT THE PRIOR WRITTEN CONSENT OF PELVALON, INC.

### **2.5.2 Fitting Metrics**

Clinicians will be asked at fitting visits, Eclipse visits, and annual renewals to provide information on the fitting process. For example, how many Inserts were used, and what sizes.

### **2.5.3 Eclipse Experience Assessment**

Subjects will be asked, at in-office visits (fitting follow-ups and 12-month visits), to provide feedback on several Eclipse Experience questions related to perceptions of device comfort, satisfaction with usage and features, and impact on daily activities. This assessment includes the Patient Global Impression of Improvement (PGI-I), a validated global index that may be used to rate the response of a condition to a therapy on a scale from 1 (Very much better) to 7 (Very much worse). The PGI-I will be used to assess improvement of accidental bowel leakage in comparison to how it was prior to joining the registry or starting with Eclipse.

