### **2.5.5 Optional 3, 6 and 9 Month Surveys**

For the completion of online surveys at interim timepoints, a single survey generated using Survey Monkey containing the Eclipse Experience Assessment and the Vaizey score will be sent to subjects via a secure e-mail link or letter for completion approximately every 3 months after registering for the study. The electronic surveys are designed in such a way that there is no way to link a specific computer's IP address to the survey responses. For patients unable or unwilling to use the online survey, paper copies can be mailed to their addresses, with a pre-paid return envelope.

Subjects will have a 4 week window during which they can complete the surveys (every 3 months +/- 2 weeks) from their Eclipse Fitting date (or renewal date). If the surveys for the associated time period are not completed within this 4 week window, they will be counted as missed data points. Subjects will receive at least one, and no more than 5, reminders (by email and/or mail) to complete the surveys throughout the 4 week window.

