### **3.2 Outcomes Measurements**

Outcomes Measurements will be assessed at 12 months. Additional assessments may be made for interim (3, 6, 9-month) time points. Where applicable, changes from baseline will be evaluated. Baseline data will be defined as data provided at the initial Fitting Visit. If the patient was previously using the Eclipse System (e.g. joins the registry at a yearly follow-up/renewal), her baseline values will be omitted, and she will be excluded from analyses that require a baseline value.

The PGI-I, assessed as part of the Eclipse Experience Assessment, assesses changes from baseline in the control of bowel leakage, but does not have a baseline measurement. Instead, it is rated on a 7-point scale, where 1 is "Very much better" and 7 is "Very much worse". For a given time point, the average PGI-I score will be computed as the mean score across all completed assessments. Other Eclipse Experience Assessment questions will be summarized descriptively.

Fitting Metrics will be collected at the fitting visits, and summarized using descriptive statistics.

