### **4.4 Monitoring**

The study will not be monitored but data will be reviewed on an ongoing basis and sites and/or subjects may be contacted by phone, email, or in writing to provide clarification of discrepant or missing data.

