#### **4.9 Data Collection and Data Management**

Study data will be collected using surveys that are designed to be completed online. The survey questions will be built using an online survey tool called Survey Monkey. A secure link will be available to the clinician and patients for use during visits, and will be sent to each patient at the interim time points via email. In some cases, patients may be unable to complete the surveys electronically in which case they may be mailed to their home address with a pre-paid return

envelope for them to complete and return the survey in hard copy format. If hard copy surveys are collected these will be data entered by either Pelvalon Clinical or other delegated representatives of Pelvalon, and the hard copy surveys will be maintained as part of the audit trail.

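### Outcomes are assessed at 12 months at an office visit, but a remote survey, window and reminders are set out only for months 3, 6 and 9, so women who stopped Eclipse may be under-represented at month 12.

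*Protocol*

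**What the plan says.** - **Time point.** Section 3.2: "Outcomes Measurements will be assessed at 12 months". Analyses at 3, 6 and 9 months are permitted but not required.
- **Place of the 12-month assessment.** Section 2.5.3, on the Eclipse Experience Assessment that contains the PGI-I: "Subjects will be asked, at in-office visits (fitting follow-ups and 12-month visits), to provide feedback". Table 2 lists this assessment, the Vaizey score and the clinician-reported Fitting Metrics in the 12-month column.
- **Remote collection.** Section 2.4: "subjects will be sent an email with a link to the optional 3, 6, and 9 month surveys". Section 4.9 says of the survey link that it "will be sent to each patient at the interim time points via email"; its other stated use is during visits.
- **Window and reminders.** Section 2.5.5, whose heading covers months 3, 6 and 9 only, gives a window of 2 weeks either side, counts later surveys as missed, and adds: "Subjects will receive at least one, and no more than 5, reminders".
- **General contact.** In section 2.3, registering signifies willingness "to be contacted by the Sponsor by phone, email or in writing to remind" subjects about surveys. Section 4.4 says that "sites and/or subjects may be contacted by phone, email, or in writing to provide clarification of discrepant or missing data".
- **Who is analysed.** Section 3.1 keeps every consenting new subject with at least an initial fitting. Section 3.2 averages the PGI-I over whichever assessments were completed.

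**The concern.** The optional time points have a defined way of reaching a woman at home, a window and a reminder count. The time point on which outcomes are assessed has none of these for a woman who stays away from the clinic.

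This matters if attendance goes with continued use. Section 1.5.3 describes a fitting period before a commitment to a year of use, so a new Insert falls due at about month 12. Section 2.5.2 has clinicians report Fitting Metrics at annual renewals, and Table 2 schedules them at month 12. A woman who never found a fit, or who gave up the device, plausibly has less reason to attend, yet she remains in the analysis set.

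The registry's stated aim is to understand real-world use. If these women are measured less often, the 12-month PGI-I and Vaizey change would describe continuing users more than all women fitted. An analysis plan can describe or model missing answers, but it cannot collect 12-month answers that were never requested.

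**Working it through.** **1. The text, time point by time point**

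| | Months 3, 6, 9 | Month 12 |
|---|---|---|
| Status | Optional (2.4, 2.5.5) | Outcome time point (3.2) |
| Emailed or mailed send | Yes (2.4, 2.5.5, 4.9) | None stated |
| Window | 2 weeks either side (2.5.5) | None stated |
| Reminders | One to five (2.5.5) | No schedule; general contact only (2.3, 4.4) |
| Payment | For completed online surveys (4.10) | Possible payment for the office visit (4.10) |

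Table 2 states that "shaded columns indicate in-office visits", but the shading cannot be seen in the text available here. The in-office status of month 12 therefore rests on section 2.5.3. The phrase about surveys every 3 months in section 2.5.5 could be stretched to month 12, but its heading, its reference to interim time points, and sections 2.4 and 4.9 all limit it to 3, 6 and 9.

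**2. Possible size**

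The protocol states no expected attendance, discontinuation, SD or precision target, so there is no planned figure to reproduce. Let m be the share unmeasured at month 12, and d the mean in unmeasured women minus the mean in measured women.

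Mean for all = (1 − m) × measured mean + m × (measured mean + d) = measured mean + m × d.

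The reported mean therefore differs from the mean for all by m × d. On the PGI-I (1 best, 7 worst), a positive d makes the reported mean too favourable.

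Input from the protocol: the cap of 150 subjects (synopsis). Assumed: m, d and SD. Measured n = 150 × (1 − m); 95% half-width = 1.96 × SD / √n.

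| m | n | Gap, d = 0 | d = 1 | d = 2 | Half-width, SD 1.0 | SD 1.5 | SD 2.0 |
|---|---|---|---|---|---|---|---|
| 10% | 135 | 0 | 0.10 | 0.20 | 0.17 | 0.25 | 0.34 |
| 30% | 105 | 0 | 0.30 | 0.60 | 0.19 | 0.29 | 0.38 |
| 50% | 75 | 0 | 0.50 | 1.00 | 0.23 | 0.34 | 0.45 |

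For example, at m = 30% and SD 1.5: 1.96 × 1.5 / √105 = 0.29, against a gap of 0.30 × 1 = 0.30.

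At d = 1 the gap equals the half-width when m × √(1 − m) = 1.96 × SD / √150. With SD 1.5 the right side is 0.240 and m is about 28%. With SD 2.0 it is 0.320 and m is about 42%.

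For Vaizey change (score 0 to 24), an assumed d of 0 to 4 points gives gaps of 0 to 0.4, 0 to 1.2 and 0 to 2.0 points at m = 10%, 30% and 50%. Its n would be below the figures above if any renewal enrollees join, since section 3.1 excludes them from baseline comparisons.

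**The case against.** The protocol does not contradict itself here. Table 2 schedules the 12-month assessment for every subject, and collecting an outcome at a visit is a common design. Several provisions support attendance or response:

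- Section 2.3 pays sites for surveys at each visit, and section 4.10 allows payment to patients for visits.
- Section 2.3 offers paper versions of all surveys to women without an email address or unwilling to give one. Section 4.9 allows mailing to those unable to respond electronically.
- The agreement to be reminded in section 2.3 has no time limit.
- Interim surveys from women who later stay away would give some information about them.

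All of this stands and reduces the problem. None of it commits to a 12-month remote survey, with a window and reminders, for a woman on the email route who does not come. The interim surveys are optional and do not supply the month 12 answer.

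It can also be said that the registry concerns women using Eclipse, so that continuing users are the right target. The design statement does use those words, but section 3.1 keeps every fitted woman in the analysis set, and the results would be read against that set.

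A reader might infer that the 12-month visit is open only to women renewing the device, or that the 12-month results will be biased. The protocol supports neither. It nowhere makes attendance conditional on continued use or says that a woman who stopped is not invited, and section 2.3 simply calls it the annual visit. The overlap with renewal is an inference from sections 1.5.3 and 2.5.2 and Table 2. A remote survey would also have non-response of its own.

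**Conclusion.** The point holds as a gap in data collection that is cheap to close, not as an error or a demonstrated bias. The protocol assesses outcomes at month 12, yet defines remote follow-up only for the optional surveys before it. Women who stopped Eclipse or were never successfully fitted may therefore be under-represented in the 12-month results.

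The size cannot be derived from the protocol. It is zero if unmeasured women fare as measured women do, and the sign reverses if they fare better. On the assumed values, a difference of 1 PGI-I point is below sampling error at 10% unmeasured. It reaches sampling error at about 28% with SD 1.5, and only at about 42% with SD 2.0. These figures show scale only, since m, d and SD are all assumptions.

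How the response share is reported, and whether new and renewal subjects are shown separately, are matters commonly left to a statistical analysis plan and form no part of this point.

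**What to change.** - **Sections 2.4, 2.5.3, 2.5.5 and 4.9:** send the existing combined Vaizey and Eclipse Experience survey at month 12 by the existing email or mail route, with the existing window and reminders. Send it to every subject in the analysis set who has not completed it in the office, whether or not she still uses Eclipse.
- **Survey content:** record current use of the device, if the questionnaire does not already do so.
- **Synopsis and section 2.3:** participation is now stated as one year, and online data capture as up to one year. Say that both run to the close of the 12-month window.
- **Section 4.10 and the consent form:** extend survey payment to month 12.

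The office visit stays for Fitting Metrics. The sponsor has a precedent: section 1.4 describes LIBERATE PRO as including a 12-month online survey with no clinic visits required.

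**Cost:** one more send of an existing survey, a few more payments, short text edits and a minor consent and IRB update. The 12-month result may look less favourable.

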### **3.1 Analysis Population**

The Analysis Data Set (ADS) will include all subjects who consent to participate in the PURSUIT registry and have at least an initial fitting, or, in the case of a patient already using Eclipse, be administered an annual renewal Eclipse.

---

 Vaizey, CJ, et al Gut 1999;44:77-80 doi:10.1136/gut.44.1.77

 Maeda Y. Does the St. Mark's incontinence score reflect patients' perceptions? A review of 390 patients. *Dis Colon Rectum*. 2008 Apr;51(4):436-42

For any analyses that require a comparison to baseline data, or data collected at the initial fitting visit, patients who enroll at their Eclipse renewal will be omitted from the ADS, as they will not have baseline or fitting metrics.

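### Section 2.5.3 gives the PGI-I two reference times and does not say which applies to women who enroll at annual renewal, for whom the two differ

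*Protocol*

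**What the plan says.** The registry takes two kinds of subject. Protocol section 2.2 puts it as "She must be a new user of Eclipse or a patient returning to the clinic for her annual f/u visit", and the synopsis likewise admits "those already using Eclipse who return for an annual renewal visit during the enrollment period". Both kinds belong to the Analysis Data Set. Section 3.1 requires an initial fitting or, "in the case of a patient already using Eclipse, be administered an annual renewal Eclipse".

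The PGI-I is part of the third outcome listed in the synopsis. Section 2.5.3 describes it as a seven-point rating of how a condition responds to therapy, and sets the comparison as "in comparison to how it was prior to joining the registry or starting with Eclipse".

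Section 3.2 says that the PGI-I "assesses changes from baseline in the control of bowel leakage, but does not have a baseline measurement". The same section states: "Baseline data will be defined as data provided at the initial Fitting Visit". For a woman who joins at renewal it drops baseline values and says that "she will be excluded from analyses that require a baseline value". The PGI-I average at a time point is then the mean over every assessment completed, with no split between new and renewal enrollees.

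**The concern.** A global impression item has meaning only relative to the state the patient is asked to recall. Section 2.5.3 names two such states, and for renewal enrollees they are not the same. A stable, well-controlled renewal user could truthfully answer 1 or 2 against her condition before Eclipse, and 4 against her condition when she joined. The first answer describes treatment benefit and the second describes benefit maintained.

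Renewal enrollees are left out of baseline comparisons, which include the change in the St. Mark's (Vaizey) score. If their PGI-I ratings are used, it is the only named measure of improvement to which they contribute. If ratings are collected without a fixed reference, no later analysis can recover which one each woman used. A statistical analysis plan could decide whose ratings enter the mean, but it could not repair the ratings themselves. Reporting the two groups separately would not be enough either, since the renewal group's own scores could still mix references.

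**Working it through.** The protocol states no PGI-I figure, target or power calculation, so there is nothing to reproduce. The check sets the sections side by side, then gauges the size on stated assumptions.

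**1. Do the two references differ?**
- *New user.* Table 2 combines enrollment and the first fitting in one visit. Joining and starting therefore fall at about the same time, and the "or" does no harm.
- *Renewal enrollee.* She already uses Eclipse when she joins. Section 1.5.3 speaks of "committing to the year-long use of the Eclipse Insert", and renewal is annual, so a first renewal comes about one year after starting, and later renewals come later still. This interval is inferred; no section states it.
- *Position at her 12-month survey.* Section 2.5.5 runs the survey clock from the fitting date or the renewal date. Her state at joining then lies about 1 year back, on Eclipse. Her state before Eclipse lies about 1 + 1 = 2 years back or more, untreated.

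**2. Does another section choose between them?** Section 3.2 ties the PGI-I to change from baseline and places baseline at the initial Fitting Visit. For renewal enrollees it omits baseline values. This does not tell such a woman which state to recall.

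**3. Do renewal ratings enter the mean?** The exclusion covers analyses that need a baseline value. Section 3.2 says the PGI-I has no baseline measurement and averages every completed assessment. On the plain reading they enter.

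**4. Size, by assumption only.** The documents give neither the share of renewal enrollees nor their scores.

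Let *p* be the renewal share among raters, and *d* the difference in a renewal user's score between the two references. If all renewal users answered against one reference rather than the other:

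shift in pooled mean = *p* × *d*

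The upper value of *d* takes a stable user who scores 1.5 against the pre-Eclipse state and 4 against the state at joining: 4 − 1.5 = 2.5, out of the 7 − 1 = 6 points on the scale. The lower value is set at 1.

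| Renewal share *p* | *d* = 1 | *d* = 2 | *d* = 2.5 |
|---|---|---|---|
| 10% | 0.10 | 0.20 | 0.25 |
| 30% | 0.30 | 0.60 | 0.75 |
| 50% | 0.50 | 1.00 | 1.25 |

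These are maxima for each pair of assumptions. If only a fraction *f* of renewal users take the joining reference and the rest take the pre-Eclipse one, the shift relative to a uniform pre-Eclipse reference is *p* × *f* × *d*. With *p* = 30%, *f* = 0.5 and *d* = 2.5 it is 0.30 × 0.5 × 2.5 = 0.375. If renewal ratings are excluded, the shift is 0.

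**The case against.** The strongest reply is that the "or" is distributive. The words about starting Eclipse add nothing for a new user, so they may have been written for existing users: new users compare with before joining, existing users with before starting. Every subject would then be referred to her pre-Eclipse state. The description of the PGI-I as a rating of response to therapy points the same way, as does placing baseline at the initial fitting. This is a sensible reading and would resolve the matter. It is not stated, though, and nothing in section 2.5.3 prevents the other reading.

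Second, section 2.5.3 describes the survey and is not the survey item. A reader might infer that the question itself is faulty, or that a renewal user's rating has no defined meaning. The documents do not support this, because the item wording is not shown and may already name one reference or branch by type of user. If it does, the protocol should match it.

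Third, a missing baseline value is not a missing reference state. The PGI-I is retrospective and needs no earlier measurement. That is right, and the point here rests on the dual reference rather than on the omitted baseline data.

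Fourth, because section 3.2 describes the PGI-I as change from baseline, the exclusion of renewal enrollees might be meant to cover it. Its statement that there is no baseline measurement, and the averaging over every completed assessment, point the other way. If exclusion is intended, the section needs to say so.

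Finally, this is an open-label registry with no stated hypothesis test or success threshold, and the PGI-I is one component of one outcome. That stands, and it limits how much weight the point can carry.

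**Conclusion.** The point holds in a limited form. The protocol names two reference times for the PGI-I and does not fix which applies to a woman enrolled at renewal. On the plain reading of section 3.2, her rating still enters the mean. This is more than missing detail: used as written, the dual reference leaves renewal ratings on a named outcome open to two incompatible interpretations.

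On the assumed ranges in the table, the pooled mean could move by at most about 0.1 to 1.25 points with no change in any patient's condition. A reader might take the upper figure as an expected bias. It is not: it needs a 50% renewal share, a 2.5-point gap built on assumed scores, and every renewal user switching reference together. A mixture gives less, and a baseline exclusion that covers the PGI-I gives none.

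This is a cheap improvement, not a flaw that undermines the registry.

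**What to change.** - In section 2.5.3 and on the survey form, use one reference for all subjects at all time points: *compared with before you first started using Eclipse*. Delete the alternative that refers to joining the registry.
- In section 3.2, describe the PGI-I as *change from before first Eclipse use* instead of as a change from baseline.
- In section 3.2, state whether renewal enrollees' ratings enter the PGI-I mean, and report new and renewal enrollees separately.

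The cost is one line of survey wording and a few sentences of protocol text. New users lose nothing, because the two times coincide for them. The downside is longer recall for renewal users, who must think back about two years or more by the 12-month survey.
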